Before being cleared to interact with participants, facilitators will be required to demonstrate competency through three mock sessions in English.

We will also train a pair of interviewers to recruit couples and conduct assessment visits. Drs. [name] and [name] will lead additional training with staff, covering topics on couples counseling, the mobile breathalyzer technology, how to handle ethical issues with couples, health education around alcohol use and HIV, the intervention manuals and procedures, and professional conduct.

5.5 Supervision. Supervision of facilitators will occur as follows. Following each session, facilitators will listen to the audio-recording in Zulu and complete a self-assessment, identifying areas they did well, struggled with, or faced challenges with couples. The HSRC research manager or their peer facilitator will also listen to audio-recordings and complete an assessment form. Study investigators will meet with the research manager to discuss the self-assessments, and supervisor/peer assessments to assess competency and identify areas for further coaching. If budget allows, we will translate and transcribe a random set of MI sessions into English for [name] to provider further training.

[name] will provide monthly supervision to staff on intervention delivery. [name] will meet quarterly with [name] to provide strategic direction and support. PI [name] will take primary responsibility for the design, implementation and analysis of the qualitative data, working with the other co-Investigators.

5.6 Fidelity monitoring of intervention. After each session, facilitators will complete a checklist to ensure each section of the intervention was covered. Intervention sessions will be audio-recorded. The HSRC manager will listen to audio files of sessions and also complete a checklist for the sessions. Self-assessment forms described above will contain rating for key MI components (e.g., collaboration, respect, etc.). A separate space on the checklist and self-assessment forms will be provided for written comments. Completed forms will be discussed in regular Zoom calls with the team to discuss areas where further guidance is needed and to help problem-solve challenges.

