5.7 Recruitment and retention. We will recruit and randomize around 120 couples to meet our target sample size of 90 couples, assuming that we will lose around 25-30% of couples after randomization. We anticipate that we will lose a very small percentage of couples due to break-ups, deaths, and migration (<5% in Uthando Lwethu), which we have accounted for in recruitment and analysis plans.

5.8 Randomization process. After informed consent and the baseline assessment, couples will be randomized to either the control arm, the couple-based MI arm, or the couple-based MI with

Couple-Based Motivational Interviewing with Mobile Breathalyzers to Reduce Alcohol Use in South Africa

mobile breathalyzers arm (MI *Plus*). We will use randomly permuted block sizes (e.g., 3, 6, and 9) generated using a computerized and secure process. The UCSF project coordinator and the HSRC data manager will use the table that the statistician created to print documents that assign participants to one of the three arms. These documents will be placed in sealed envelopes and maintained by the HSRC data manager. HSRC interviewers will take a small subset of envelopes into the field with them. At the end of the baseline survey, the index patient will be given the envelope that contains the random assignment. Couples will receive an appointment card with a date for their next study visit following randomization.

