A technology navigator will monitor daily compliance and check-in with participants to assist with login credentials, lost or damaged devices, cellular connectivity, difficulties using the phones or breathalyzers, and intentional non-use of the breathalyzers—with close monitoring during the first week. Navigators will monitor for safety issues and IPV (interpersonal violence) during routine check-ins and will provide assistance should a safety/IPV issue arise.

5.11 Survey assessments. Assessment visits will be held in community-based locations such as youth centers or in our team's mobile caravans used in other couples' studies. To minimize loss-

Couple-Based Motivational Interviewing with Mobile Breathalyzers to Reduce Alcohol Use in South Africa

to-follow-up, we will administer follow-up surveys over the phone in the case that a participant moves out of the area or is unavailable for an extended period of time. For the pilot study, surveys will be administered at baseline and 2-months (after receiving all MI sessions and/or using the breathalyzers for 60 days), and 6-months post-intervention initiation. Measures collected will be the same across visits with the exception of time-invariant variables such as demographics (collected at baseline only). All measures will be pre-tested, tailored for South Africa, and translated to *isiZulu* and back-translated to English. See Appendix with full survey instrument. Survey assessments will be interviewer-administered on tablet devices using REDCap mobile, last around 90 minutes, and uploaded to a secure web-based storage system. Partners will be assessed separately, but simultaneously, in private interview rooms.

	Domain	Measure (alphas noted are from prior studies with couples)
Primary outcomes (future trial)	Alcohol use	Number of drinking days in past 21, assessed using the three-week timeline follow-back method (TLFB) confirmed with the PEth biomarker.[32] AUDIT-C positive (score of ≥ 4 for men and ≥ 4 for women) and/or PEth positive (≥ 35 ng/ml).[33, 34]

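### Interviewers who enrol couples also carry the allocation envelopes and run the assessments; concealment and assessor blinding rest on safeguards that the plan does not state

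*Combined protocol and SAP*

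**What the plan says.** On roles, section 5.4 states: "We will also train a pair of interviewers to recruit couples and conduct assessment visits".

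On allocation, section 5.8 gives this sequence:
- The list is computer-generated: "We will use randomly permuted block sizes (e.g., 3, 6, and 9) generated using a computerized and secure process".
- Assignments are printed from the statistician's table, and "These documents will be placed in sealed envelopes and maintained by the HSRC data manager".
- Then "HSRC interviewers will take a small subset of envelopes into the field with them".
- Timing is after consent and baseline: "After informed consent and the baseline assessment, couples will be randomized to either the control arm". The handover is described as "At the end of the baseline survey, the index patient will be given the envelope that contains the random assignment".
- Finally, "Couples will receive an appointment card with a date for their next study visit following randomization".

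On outcome collection, section 5.11 states: "Survey assessments will be interviewer-administered on tablet devices using REDCap mobile". Its table puts drinking days in the past 21, by timeline follow-back (TLFB) and confirmed with PEth, first among the alcohol outcomes. Section 5.13 describes PEth collection at the 2-month visit. Section 8.3 adds that interviewers are gender-matched and that each deals with only one member of a couple.

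**The concern.** Allocation concealment works when the person enrolling a couple can neither foresee nor influence the next assignment. Here that person holds a stock of assignments away from the office. Nothing in the text fixes which envelope goes to which couple or would later show that the order was kept. The interviewer is also likely to know the arm when asking about drinking at 2 and 6 months, and interviewer-administered self-report is open to influence from that knowledge.

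This matters in a pilot because Aim 2 is to develop and pilot test the randomization procedures for the future trial, so the procedure is itself a product of the study. The only randomization indicator in Table 4 is that 90% of enrolled couples complete the process. An allocation with envelopes used out of order would still pass. The monitoring in sections 9.1.3 and 9.2 covers interview standardization, recruitment, missing data and follow-up, not allocation order. H1 and H2 (section 7.3) compare reductions in drinking days between arms at alpha .05, so they are the results that differential reporting could distort.

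**Working it through.** The plan gives no figure to reproduce. The check sets the sections side by side and then sizes the possible routes.

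**1. Who does what.** Section 5.4 joins recruiting and assessing in one pair of interviewers. Section 5.8 gives interviewers the envelopes. Section 5.11 has interviewers administer the surveys. With a single gender-matched pair, each seeing one partner (section 8.3), the person present at allocation is probably the one who asks the follow-up questions. That the interviewer learns the arm is an inference: the handover closes the interviewer's own visit, an appointment card follows, and nothing shields the arm.

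**2. Predictability from blocks.** Inputs: three arms and block sizes 3, 6 and 9 (section 5.8, given as examples); equal frequency of the sizes is assumed. An assignment is fully determined when only one arm is left in its block. The expected number per block is the expected length of the closing run of identical assignments:
- size 3: 1
- size 6: 1 + 1/5 = 1.2
- size 9: 1 + 2/8 + (2/8)(1/7) = 1.286

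The share is (1 + 1.2 + 1.286)/(3 + 6 + 9) = 3.486/18 = 19.4%. This requires knowing where each block begins and ends, and random variation in size hides that.

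With boundaries hidden, I simulated lists of 120 couples for an observer who knows the possible sizes and every past allocation in order. An assignment counted as determined if every block layout compatible with the history left the same arm. The share is about 4%, or about 5 of 120 couples (0.04 × 120 = 4.8), against about 23 (0.194 × 120) with boundaries known. The same observer, always guessing the least-used arm so far, is right about 55% of the time, against 33% by chance. Two interviewers with separate stocks would see less than this observer.

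**3. Choice among held envelopes.** The number carried is not stated. With k in hand, the chance that at least one holds a given arm is about 1 − (2/3)^k: 56% for k = 2, 70% for k = 3, 87% for k = 5, against 33% for one fixed next envelope. This is usable only by someone who knows the contents. Picking among sealed envelopes of unknown content creates no selection.

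**4. Unblinded interviewing.** Assume no true effect, 30 index drinkers per arm (section 2.5), a two-sided 5% test (sidedness is not stated), and self-report that differs between arms by b SD through knowledge of the arm. The standard error is √(2/30) = 0.258 SD. The rejection rate is 1 − Φ(1.96 − b/0.258) + Φ(−1.96 − b/0.258).

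| b (assumed) | Rejection rate |
|---|---|
| 0 | 5% |
| 0.1 | 7% |
| 0.2 | 12% |
| 0.3 | 21% |
| 0.5 | 49% |

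The documents give no value for b. The table shows sensitivity, not an estimate.

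**5. Reach of the objective check.** Section 5.13 describes PEth at 2 months, with no baseline or 6-month sample. Section 3.1 mentions draws at follow-up visits for couples with two heavy drinkers on ART. Section 5.11 allows telephone follow-up, which cannot yield a finger prick. PEth can therefore support the 2-month comparison between arms but, as described, cannot verify change from baseline or the 6-month reports.

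**The case against.** The plan has real safeguards: a secure computer-generated list, varying block sizes, sealed envelopes kept centrally, allocation after consent and baseline, and a laboratory marker at the end of the intervention. Enrolment and baseline answers are settled before the envelope changes hands. Section 3.2 refers to a team of recruiters, so others may also recruit. The primary analysis is descriptive feasibility against thresholds, largely counts and logs, and the alcohol comparisons are exploratory. All of this stands and limits the consequence.

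Three stronger readings are tempting, and the documents do not support them.
- A reader might infer that interviewers can choose the arm for any couple. The text neither states nor excludes numbered or couple-linked envelopes, and choice matters only if the contents are known.
- A reader might infer that a fifth or a third of assignments are predictable. The first needs known block boundaries; the second needs every block to be of size 3, which section 5.8 does not describe. Using envelopes out of order would also lower predictability, so the two mechanisms do not add up.
- A reader might infer that the results will be biased towards the intervention. No direction or size of selection is shown.

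What the objection does not remove is that a field-held stock leaves the order of use in the hands of those who enrol, with no record stated that could show it was kept.

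**Conclusion.** The point holds as a weakness of procedure, not as demonstrated bias. Concealment depends on interviewers who also enrol and assess, and assessor blinding is not addressed. Block predictability is a minor contributor. The larger issues are the untracked envelopes and self-report collected by staff who probably know the arm. An assumed reporting difference of 0.2 SD would raise the error rate of H1 or H2 from 5% to about 12%.

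The conclusion rests on two inferences: that the interviewer present at handover learns the arm, and that the same pair conducts follow-up. If the site already numbers and logs its envelopes, or keeps follow-up interviewers from the arm, stating so would settle most of the point. Since Aim 2 pilots these procedures, the change should be made, but the descriptive feasibility analysis does not depend on it.

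**What to change.** 1. Replace the field-held envelopes. Release each assignment from a REDCap randomization table only after both partners' baseline surveys are submitted. When there is no signal, the interviewer phones the HSRC data manager, who reads out the next assignment.
2. If envelopes stay, make them opaque and sequentially numbered, write the couple ID on the sealed envelope before it is opened, and reconcile the used numbers against the list.
3. State in section 5.11 that follow-up interviewers are unblinded, unless they are kept from the arm, in which case say how.
4. Report 2-month PEth by arm alongside self-reported drinking as the objective check on H1 and H2.

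The cost is small. REDCap already carries the surveys (section 5.11), the data manager already maintains the envelopes, and neither sample size nor visits change. The downsides are occasional delay without signal (the upload speeds in section 2.1 go as low as 0.05 Mbps, hence the phone route) and that some participants will still reveal their arm at follow-up.

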2.5 Study design

For Aim 1, we will adapt a couple-based MI framework and interventions developed by co-I [name] (*We Test* and the *Couples Health Project*) to address alcohol use in heavy alcohol users and their primary partners and incorporate the mobile breathalyzer component. We will follow the ADAPT-ITT framework by conducting focus group discussions (FGDs) with around 40 key stakeholders to gain feedback on the intervention and then refining the intervention. For Aim 2, we will develop training procedures, study procedures, and data collection instruments that will be pilot tested during the RCT. For Aim 3, we will conduct a three-arm RCT with 30 couples randomized to the following arms (90 couples total): 1) an enhanced usual care control condition; 2) couple-based MI; and 3) couple-based MI with mobile breathalyzers for real-time feedback. For arm 2 and 3, couples will receive 3 MI sessions over a 60-day period with an experienced counselor to help strengthen communication and problem-solving skills around alcohol use. For Arm 3, couples will use the mobile breathalyzers and app for 60 days and receive the same MI sessions, which will also incorporate feedback on BAC levels (prior 30 days) and teach couples how to effectively engage with the breathalyzers. This design will allow us to assess the effectiveness of couple-based MI alone and the added synergistic effect of the mobile breathalyzers on alcohol use and HIV outcomes (e.g., adherence to antiretroviral therapy (ART), viral suppression). Our F&A outcomes will include enrollment and retention rates, satisfaction with both intervention arms, MI session attendance rates, and follow-up survey completion rates. We will also conduct qualitative interviews with a subset of 15 couples to contextualize F&A data and refine the intervention and procedures for a future full-scale efficacy trial.

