Secondary outcomes (future trial)	Viral suppression and ART adherence	Viral suppression will be defined as less than 1000 copies/mL for DBS viral load. ART adherence will be captured using the bean method for low-literacy populations[35], by placing beans in a bowl for the number missed pills in the past 30 days. We will dichotomize adherence using a 95% cutoff, based on data showing that patients who miss $\geq 5\%$ of doses have worse virologic outcomes.[36]
	Couple communication	Constructive, avoidant, and demand-withdraw communication (communication patterns questionnaire; $\alpha=0.69-0.72$).[37]
	IPV	Physical, sexual, and emotional violence (WHO domestic violence measure; validated among PLWH; $\alpha=0.75-0.83$).[38, 39]
	Relationship dynamics	Trust (dyadic trust scale; $\alpha=0.82$).[40] Intimacy (emotional intimacy subscale of Sternberg love scale; $\alpha=0.90$).[41] Unity (inclusion of self-in-other measure).[42] Relationship satisfaction (couple satisfaction index, single item).[43] Sexual satisfaction (couple sexual satisfaction scale; $\alpha=0.89$).[44]
Mediating variables (future trial)	Shared illness appraisal	Single item that asks: "When you think about problems related to your [or your partner's] alcohol use, to what extent do you view this as "our problem" [shared by you and your partner equally] or mainly your [your partner's] own problem?".[45]
	Communal coping	Dyadic coping inventory, modified for alcohol use.[46, 47] Partners are asked how often they, as a couple, engage in activities to deal with alcohol (e.g., "We try to cope with alcohol issues together and search for solutions").
	Alcohol social support	Alcohol-specific partner support (to be adapted from the Social Provision Scale).[48]
Covariates (future trial)	Socio-demographics	Gender, age, marital status, relationship length, religion, living children, education level, household asset index.[49]

5.12 Medical record extraction. For participants living with HIV, we will access their medical record information including recent HIV results. We will obtain this information from electronic HIV registries (e.g., Tier.Net) or online databases (e.g., National Health Laboratory System), or

Couple-Based Motivational Interviewing with Mobile Breathalyzers to Reduce Alcohol Use in South Africa

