7.3 Hypotheses and methods for preliminary/exploratory analyses. Although the purpose of this study is to determine F&A rather than to conduct formal hypothesis tests, we will evaluate exploratory hypotheses as part this assessment process. For example, we expect that: H1) participants in the couples MI-only group (arm 2) will report a greater reduction in the number of drinking days (confirmed with PEth) than participants in the control group (arm 1); H2) participants in the couples MI with mobile breathalyzers group (arm 3) will report a greater reduction in the number of drinking days than participants in the couples MI-only group (arm 2). Secondarily, we also anticipate that intervention participants will report a higher odds of adherence to ART and viral suppression than those in the control arm. We also anticipate the intervention participants will report higher (indicating more positive) scores on communication and relationship dynamics and less intimate partner violence than those in the control arm. Reflecting the exploratory nature of these analyses, alpha will be set at .05 for all inferential analyses.

7.4 Power analyses. Formal tests of health outcomes or attempts to obtain valid estimates of effect sizes are not statistically justified for the proposed study. Pilot studies, by design, cannot definitively test hypotheses due to their smaller sample sizes and the frequent design adjustments necessary to maximize recruitment, retention and quality assessment of outcomes. Effect size estimates are not sufficiently reliable given the breadth of the confidence intervals. However, to supply additional information, we conducted several power analyses using NCSS PASS. In sum, our study is powered to detect small to medium distances to confidence limits for descriptive statistics and medium to large longitudinal analysis effects, though, as noted above, formal hypothesis testing will not be the focus of this F&A study.

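### ART adherence is collected as a 30-day count of missed pills, but the only analysis described is a 95% cut; add a baseline-adjusted analysis of the count beside it

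*Combined protocol and SAP*

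**What the plan says.** The outcome table in section 5.11 lists ART adherence among the secondary outcomes for the future trial. It is measured by the bean method, "by placing beans in a bowl for the number missed pills in the past 30 days". The same cell continues: "We will dichotomize adherence using a 95% cutoff". The reason given is virologic: the cut is "based on data showing that patients who miss" at least 5% of doses do worse virologically.

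Section 5.11 also says that the measures are the same at every visit apart from time-invariant items, so a baseline count exists for each participant on ART, with repeats at 2 and 6 months.

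Section 7.3 expects that "intervention participants will report a higher odds of adherence to ART and viral suppression than those in the control arm", and adds that "alpha will be set at .05 for all inferential analyses". No section describes an analysis of the count or of percent adherence.

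On size, section 2.5 plans a "three-arm RCT with 30 couples randomized to the following arms (90 couples total"). Section 7.4 gives power in words only, with nothing specific to adherence. Section 7.2 makes feasibility and acceptability the primary objective.

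**The concern.** A count with up to 31 possible values is reduced to two classes, and the boundary lies near one end of the scale. Changes that stay on one side of it are invisible to the stated analysis, however large; a change of one pill across it counts in full. In heavy drinkers, some of whom may miss many doses, a real improvement that stops short of near-perfect adherence would not show.

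At stake is what the pilot can say about adherence. Any comparison at 30 per arm is imprecise, and the next trial needs to know whether a 95% cut or the count is the better outcome. The stated analysis alone cannot answer that, although the data to answer it are collected.

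**Working it through.** There is no power or effect size for adherence in the plan, so there is no stated figure to reproduce.

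**What the cut does.** Assume one pill a day; the plan does not say. Missing 1 of 30 gives 29/30 = 96.7%, adherent. Missing 2 of 30 gives 28/30 = 93.3%, not adherent. So 0-1 missed is one class and 2-30 the other. A change from 15 to 3 missed is a move from 50% to 90% adherence and scores as no change. A change from 2 to 1 scores as a success. This step needs no distribution.

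**What it costs.** Inputs from the plan: 30 per arm (section 2.5) and alpha 0.05 (section 7.3; two-sided assumed). Assumed: one index patient per couple contributes, no dropout, counts capped at 30 and, except in the last row, missed pills negative binomial with mean m and dispersion k. Each case was simulated with 3,000 or more trials, comparing a Mann-Whitney test on the count with a chi-square test on 0-1 against 2 or more missed.

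Information kept by the cut = ((1.96 + z for power of the cut) / (1.96 + z for power of the count))².

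| Assumed case (control v intervention mean) | Controls adherent | Power, count | Power, cut | Information kept |
|---|---|---|---|---|
| k=0.6, 4 v 1.5 | 45% | 54% | 42% | 0.72 |
| k=0.6, 6 v 2 | 37% | 66% | 47% | 0.63 |
| k=1, 3 v 1 | 44% | 81% | 69% | 0.76 |
| k=0.3, 2 v 0.5 | 68% | 49% | 48% | about 1 |
| k=0.2, 3 v 0.5 | 68% | 50% | 50% | about 1 |
| k=0.3, 1.5 v 0.5 | 73% | 32% | 32% | about 1 |
| k=0.2, 1 v 0.4 | 82% | 18% | 19% | about 1 or more |
| Mixture, adherent share 50% v 80% | 50% | 55% | 69% | above 1 |

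Worked example, second row: z for 47% is -0.075 and for 66% is 0.412, so (1.885/2.372)² = 0.63, a loss of 37%. The first three rows lose 28%, 37% and 24%. The ratios come from unrounded powers. Repeat runs moved the powers by about 1 to 2 percentage points, so differences of that size mean nothing.

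In the mixture, the intervention changes only the share of participants with 0-1 missed, and the spread within each class is the same in both arms. The power of the cut can be checked by hand. The pooled share is 0.65, so the null standard error is √(2 × 0.65 × 0.35/30) = 0.123. The alternative standard error is √((0.25 + 0.16)/30) = 0.117. Then (0.30 - 1.96 × 0.123)/0.117 = 0.50, which gives 69%. The 55% for the rank test depends on the spread within each class; it was obtained again with 0-1 equally likely among the adherent and 2-10 equally likely among the rest. An effect on never missing a pill does not always favour the cut: with a never-missing share of 30% v 65% and the rest negative binomial (mean 5, k=1), power was 57% for the rank test and 49% for the cut.

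**Sensitivity to the comparator.** Against the full negative binomial or Poisson likelihood with known dispersion, rather than a rank test, the loss ranged from 30% (Poisson, mean 1) to 85% (Poisson, mean 5). A normal measure cut at the median loses 36%, and more at any other split, but a skewed, bounded count need not behave like that.

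**The case against.** The best case for the plan has four parts.

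- The threshold is prespecified and carries a cited virologic reason, so it is not a data-driven split. This stands, and it is why the indicator should stay. It does not show that differences on either side of the threshold are uninformative, and viral suppression is already measured directly as a binary outcome.
- The outcome is exploratory. Section 7.4 says that formal tests of health outcomes are not statistically justified here, and no feasibility decision turns on adherence. This stands and sets the severity. It does not remove the point, because section 7.3 still plans inferential analyses at 0.05 and section 5.11 carries adherence forward to the future trial.
- The size of the loss is unknown. This stands. A reader might infer from the first three rows of the table that the cut throws away a fixed quarter to a third of the information. The documents give no missed-pill distribution, adherence rate or effect size, and other plausible assumptions give no loss or a gain. Nor does the small arm size drive the percentage: it limits absolute power, not the share of information lost to the cut.
- Nothing is lost for good. This also stands. A reader might infer that the pilot could not supply a variance for the next trial, but the count is recorded and its mean and spread can be computed at any time. Likewise, the plan does not say that the dichotomy is the only permitted analysis; it is simply the only one described.

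**Conclusion.** The point holds in a limited form. The plan collects a count, describes only a 95% dichotomy with an odds hypothesis, and so names an analysis that can be blind to large changes in missed doses. Under the stated assumptions, the loss against a rank test lies between about none and about 37%: near none when counts are highly skewed and most controls already miss 0-1 pills, and 24-37% when about 37-45% of controls are adherent. When the effect is mainly a move across the threshold, the cut can be the more powerful analysis. The results assume one pill a day, full data on 30 index patients per arm and the distributions shown, none of which the plan supplies.

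The documents do not support the stronger readings that the 95% cut is unjustified or that it should be displaced. The case is for having both analyses. It is a cheap improvement of low severity.

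**What to change.** In section 5.11, define the number of missed pills in the past 30 days (or percent adherence, with its denominator of prescribed pills) as an adherence measure beside the 95% indicator. In section 7.3, add a prespecified exploratory comparison of that measure between arms, adjusted for its baseline value, using one named method: rank-based, ordinal or negative binomial. Report the distribution of the count by arm and visit, so that the next trial can judge which form of the outcome serves it better. Keep the 95% indicator and its stated reason.

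The cost is wording in two sections; no new data are needed. The downside is one more exploratory result to report, and little or no gain if most participants already miss 0-1 pills.
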